1

## TRIAL SUMMARY

Trial Title	Feasibility of a randomised controlled trial of a group programme for men who are concerned about their behaviour in relationships with women: pilot study		
Internal ref. no. (or short title)		Group programme for men who are concerned about their behaviour in relationships with women: a pilot trial	
Phase	pilot trial		
Trial Design	Individual randomisation		
Trial Participants	Men aged 21 and over and th partners (aged 18 or over)	Men aged 21 and over and their female partners or expartners (aged 18 or over)	
Planned Sample Size	36 men plus their current or e sample size of up to72)	36 men plus their current or ex-partners (a total planned sample size of up to72)	
Treatment duration	The intervention programme i	The intervention programme is for 26 weeks	
Follow up duration	Up to 9 months	Up to 9 months	
Planned Trial Period	March 2017 – September 201	March 2017 – September 2018	
	Objectives	Outcome Measures	
Primary	Sufficient men and partners recruited in order to meet progression criteria	Number of participants	
Secondary	Sufficient men and partners retained and followed up in order to meet progression criteria	Number of participants	

## FUNDING AND SUPPORT IN KIND

FUNDER(S)	
NIHR	Financial
Ref: RP-PG-0614-20012	Programme Grant for Applied Research
Programme Manager: [name]	

## ROLE OF STUDY SPONSOR AND FUNDER

The Sponsor (University of Bristol) oversee the regulatory and governance procedures are in place before, during and after the trial. The Sponsor ensures that the design of the study meets appropriate standards and that arrangements are in place to ensure appropriate conduct and reporting. This includes the safety and welfare of research staff (employees).

The Department of Health have prepared a contract between Bristol CCG (the grantholders) the University of Bristol (the provider) and other parties. The contract outlines the responsibilities of the funder.

## ROLES AND RESPONSIBILITIES OF TRIAL MANAGEMENT COMMITEES/GROUPS & INDIVIDUALS

• Programme Steering Committee

The PSC will provide the overall supervision of the pilot trial, functioning as its TSC. It is completely independent of the investigators, their employing organisations, funders and sponsors. It will meet 2-3 times per year.

Chair: [name]

Data Monitoring and Ethics Committee

The DMEC will assess, at intervals, the progress of the pilot and safety data, and to recommend to the TSC and the sponsor whether to continue, modify, or stop a trial. It is completely independent of the investigators, their employing organisations, funders and sponsors. This committee will meet 2-3 times per year and be available in order to oversee any decisions regarding ethical considerations that occur throughout the trial.

Chair: [name]

• Trial Management Group

The Trial Management Group will meet 4 times a year to ensure all practical details of the trial are progressing and working well and that everyone within the trial understands them. This group will be formed by the following, in addition to other members of our Programme Advisory Group.

Members: [name] (CI), [name] (Programme manager), [name] (workstream lead), [name] (research fellow), [name] (statistician), [name] (Statistician), [name] (economist), data manager, [name] (Respect research director), representative from service provider, representatives from women and men PPI groups, respectively.

Chair: [name]

### **KEY WORDS**:

Domestic violence and abuse (DVA) Perpetrator and victim/survivor Randomised controlled trial Domestic violence perpetrator programme (DVPP) Complex intervention Mental health

9

## LIST OF ABBREVIATIONS

Define all unusual or 'technical' terms related to the trial. Add or delete as appropriate to your trial. Maintain alphabetical order for ease of reference.

,	
AE	Adverse Event
CI	Chief Investigator
CRF	Case Report Form
DMEC	Data Monitoring and Ethics Committee
DVA	Domestic violence and abuse
DVPP	Domestic violence perpetrator programme
GCP	Good Clinical Practice
ICF	Informed Consent Form
IDMC	Independent Data Monitoring Committee
ISF	Investigator Site File
ISRCTN	International Standard Randomised Controlled Trials Number
NHS R&D	National Health Service Research & Development
NICE	National Institute for Health and Care Excellence
NIHR	National Institute for Health Research
PI	Principal Investigator
PIS	Participant Information Sheet
QA	Quality Assurance
QC	Quality Control
RCT	Randomised Controlled Trial
REC	Research Ethics Committee
REPROVIDE	Reaching Everyone: Programme of Research on Violence in diverse Domestic Environments
SAE	Serious Adverse Event
SDV	Source Data Verification
SOP	Standard Operating Procedure
SSI	Site Specific Information
TMG	Trial Management Group
TSC	Trial Steering Committee
TMF	Trial Master File

- All participants will be contacted 2 weeks prior to follow-up due date to check informed consent and remind of participation.
- A selection of participants will be invited for interview during the study (see section 19 - qualitative interviews)

## Feasibility of a randomised controlled trial of a group programme for men who are concerned about their behaviour in relationships with women: pilot study

#### 1. BACKGROUND

Domestic violence and abuse (DVA), is defined as any incident or pattern of incidents of controlling coercive or threatening behaviour, violence or abuse between people aged 16 or over who are or have been intimate partners or family members, regardless of gender or sexuality. DVA poses a major public health and clinical challenge to the NHS is associated with health problems in victims, perpetrators, and their children, including poor physical health, long-term illness or disability, and poor mental health, at an annual cost to the NHS of 1.8% of total budget with even greater societal costs. The NHS (and health services internationally) have not responded adequately to this need. There is growing recognition of its impact on women and children, but virtually no recognition by clinicians of men as victims or perpetrators and little research on effective interventions for men in healthcare settings. The evidence reviews in the NICE DVA guidelines identify evidence gaps with regards to an integrated healthcare response and effective interventions targeted at perpetrators.

This pilot trial forms part of an NIHR Programme grant called Reaching Everyone: Programme of Research on Violence in Diverse Domestic Environments (REPROVIDE) and builds on previous work undertaken as part of the PROVIDE Programme (see http://www.bris.ac.uk/social-community-medicine/projects/provide/). We have undertaken an evidence synthesis to: i) identify the perpetrator group model with the greatest likelihood of effectiveness in reducing perpetration of DVA and increasing the safety of victims and their families; ii) identify components of other models that are likely to improve outcomes for survivors; iii) to refine our hypothesised causal pathway and logic model as well as inform our choice of outcome measures for the intervention trial.

Following a series of expert consultation and consensus meetings, we are now at the stage of taking the evidence of what works to adapt an existing domestic violence perpetrator programme (DVPP) and to pilot and test this as an intervention for men who perpetrate violence and abuse against their female partner(s) or ex-partner(s).

The rationale for this pilot trial is that, despite the ubiquity of perpetrator programmes in the UK, Europe and North America, there is still uncertainty about their effectiveness. There is a dearth of experimental studies both internationally and outside of north America. The health impact of DVA makes provision of effective perpetrator programmes to prevent further violence a legitimate part of healthcare services. With the move towards evidence-based commissioning of health services, we need to rigorously test programmes particularly with regards to safety and health outcomes for victims/survivors, but also for perpetrator behaviour. A major research recommendation of the NICE DVA guidelines is determining the effectiveness of perpetrator interventions in terms of victims' safety, across levels of risk, and including diverse and marginalised groups.

There will be a nested qualitative study within this pilot phase to explore processes of the intervention through observations/interviews to explore the intervention acceptability and adherence which will help to inform interpretation of the trial findings. This will also improve understanding of the needs of men (and their partners) who do not fulfil our trial inclusion criteria (e.g. in same sex relationships or unable to read English), but who may contact us in the recruitment process.

The overall objective of this pilot trial is to determine the acceptability and feasibility of the perpetrator programme intervention and trial design.

#### 2. Rationale

Trials of DVPPs are challenging, from recruitment and retention of participants (perpetrators and their ex/partners) to adherence to the intervention. We will pilot an adapted DVPP intervention and the trial design, in particular assessing: the acceptability of the programme to perpetrators and victims/survivors of DVA, the feasibility of recruitment and follow up, and the completeness of outcome measure completion, with pre-specified criteria for proceeding to the full trial. This will be piloted in the greater Bristol area (including South Gloucester and North Somerset which has the infrastructure and referral pathways for a group programme (including the support for ex/partners from a domestic violence agency – Next Link) and that the agency delivering the programme (Splitz) is willing to adapt it to the intervention specification.

The programme length will be 26 weekly sessions over 26 weeks and the groups will be run on a rolling basis (i.e. as men finish the course, new men will join). A rolling programme improves the efficiency of the intervention and allows modelling of good behaviour by men who are nearing the end of the programme to men who have just joined it.

Eligible men will be allocated by a minimisation programme with a probabilistic component. Minimisation factors will be age, severity of previous violence and whether they are still with their partner. The allocation system will be constructed and, as necessary, monitored independently of the research team,

#### 2.1 Assessment and management of risk

Conducting research in this population is not without risk to the participants, the researchers and the programme facilitators. The potential risks associated with this trial and more widely in our research group, have been considered and guidance has been produced to minimise/mitigate these risks. An extensive standard operating procedure (SOP) has been developed and is available as appendix 1. All research staff will be familiarised with this SOP prior to conducting any trial-related procedure.

#### 3. OBJECTIVES AND OUTCOME MEASURES/ENDPOINTS

#### Objectives:

(i) To recruit and randomise 36 male perpetrators. *Two thirds* of the men (24) will be randomised to a community-based perpetrator programme and **one third (12)** to the control normal care group.

(ii) To recruit female partners / ex-partners of the men who have been accepted onto the study.

(iii) To measure recruitment rate, adherence of participants, fidelity of intervention and retention, and improvement in safety or feelings of safety for partners and ex-partners(iv) Identification of main cost drivers;

(v) To determine the acceptability of the intervention to perpetrators, and to their partners and ex-partners, the willingness for all participants to be randomised, the suitability of the primary outcome measure and the motivation for participation.

## 3.1 Primary objectives

The recruitment, randomisation and retention of 36 male perpetrators who will be randomised to either a 26 week weekly community-based perpetrator programme or control arm plus recruitment of their partners / ex-partners with up to a 9 month follow up in order to meet progression criteria.

## 3.2 Secondary objectives

- 1. Assess questionnaire completion
- 2. Develop fidelity framework for intervention
- Identify and pilot the collection resource use data and the associated unit costs for cost effectiveness analysis
- 4. Determine acceptability of the intervention to perpetrators, associated victims/survivors and staff
- 5. Assess the willingness and risks faced by female partners and ex-partners to be involved in the pilot trial
- 6. Explore ways of improving retention in both the intervention and control arms for male and female participants
- 7. Assess the mechanisms of support and supervision needed for those involved in the delivery of the intervention

## 3.3 Exploratory endpoints/outcomes

Objectives	Outcome Measures	Timepoint(s) of evaluation of this outcome measure (if applicable)
Trial: To assess recruitment and randomisation rate of men and their (ex) partners.	Number recruited and randomised in pilot trial	During 9 months
Trial: To assess retention of men and their (ex) partners.	Number retained during follow- up period.	During 9 months
Trial: To assess questionnaire completion	Completed data sets from PHQ-9, GAD-7, PTSD, EDQ5 and SF12 scale. Impact Toolkit questionnaire completion.	3, 6 and 9 months post randomisation.
	ICECAP-A capability measure	At 9 months post randomisation only
Trial: To develop fidelity framework for intervention	A method to assess fidelity in the main trial	During 12 months

Trial: Identify and pilot the collection resource use data and the associated unit costs	Best method for collecting data on use of health and social care services and other related costs associated with the trial.	During 12 months
Intervention: To determine the acceptability of the intervention to perpetrators, associated victims/survivors and staff.	Qualitative interviews	Time points throughout the 18 month pilot trial.
Trial: Assess the willingness and risks faced by female partners and ex-partners to be involved in the pilot trial	Impact toolkit questionnaire; qualitative interviews; collection of adverse incidents/adverse events/serious adverse events	Time points throughout the 18 month pilot trial.
Trial: Explore ways of improving retention in both the intervention and control arms for male and female participants	Engagement with PPI groups; qualitative interviews	Time points throughout the 18 month pilot trial.
Intervention Assess the mechanisms of support and supervision needed for those involved in the delivery of the intervention	Qualitative interviews and feedback sessions.	Time points throughout the 18 month pilot trial

## 4 TRIAL DESIGN

This will be a pragmatic, parallel group individually randomised controlled pilot trial. We will be testing the feasibility and acceptability of the domestic violence perpetrator programme as well as the trial.

The domestic violence perpetrator programme (DVPP) will consist of a 26-week programme incorporating 22 weekly group sessions and 4 individual sessions. The sessions will be run by two experienced DVPP facilitators (one male and one female in order to model good gender role behaviours). The programme will start as a rolling programme, allowing new intakes of participants to join at specified intervals but after six months will become a closed programme, meaning that no new men will be able to join. This is to ensure that men will have completed the programme before the end of the pilot trial and to allow sufficient time for post-completion follow-up.

The weekly group sessions will incorporate most of the elements which exist in standard DVPPs. These include: goal identification and goal setting; recognising abuse; denial and minimisation; intents of violence; basic anger management; identifying urges to perpetrate abuse and cooling-down strategies; basic CBT; effects of DVA on partners and children; participant's own childhood experiences; impacts on children; active listening; conflict resolution; masculinity; beliefs and expectations; sexual respect; attachment styles; building empathy; loving relationships; emotional abuse; accountability.

Two pre-group individual sessions will assess suitability for the programme, will assess risk, and enable a needs assessment, and will begin relationship-building.

The remaining individual sessions will be tailored for participants' needs following the initial and ongoing assessment. Possible individual interventions might include deconstructing specific incidents of abuse; accountability letters or planning discussions with partner or children; relaxation or emotional regulation work.

New participants will only be able to join the group programme in specific weeks in order to minimise disruption to men already on the programme and to ensure that new men do not join in particularly challenging weeks (such as 'sexual respect). If there is a gap of more than two weeks between assessment and the next planned intake week, individual sessions will be scheduled in order to help the participants feel engaged with the programme and to reduce drop-out between assessment and programme start.

Unemployed or low-waged men will be able to claim reasonable travel expenses associated with the cost of participating in the research programme.

## 5 STUDY SETTING

This study will be community based.

Initial meetings with potential participants to check eligibility and seek consent will be arranged in a mutually convenient location for the researcher and participant. This is likely to be within a community wellbeing organisation, health or social care building, or university building. Care will be taken when recruiting men and women – see appendix 1. The intervention programme provider coordinator will organise a risk assessment in a similar location for men.

The group programme intervention will be run out of a central Bristol community setting. It is anticipated that this space will be rented on a weekly basis rather than being a permanent base for the duration of the trial.

Partners or ex-partners of male participants who consent to join the study will be contacted by a DVA advocate based in Next Link and will have contact with that advocate at Next Link or other safe settings

## 6 ELIGIBILITY CRITERIA

#### 6.1 Inclusion criteria for male participants

- > 21 years of age
- Use of abusive behaviour in current or previous relationships with women partner(s) or ex-partner(s) and concerned about that behaviour
- Ability to read and complete outcome questionnaires

#### Inclusion criteria for partners/ex-partners

- Female partners or ex-partners of men using violence/abuse in their relationships
- >18 years
- Ability to read and complete outcome questionnaires

Protocol version 2.0 09/02/2018\_track changes

IRAS Project ID: 178666

NB the difference in minimum ages between men and women has been discussed and the expert opinion is that younger men who abuse (pre-21) often aren't so ready to change and the younger age group of men report having qualitatively different types of relationships with women e.g. including abuse and use of internet and social media and in this way the younger men can't and don't relate as well to all the other men of older ages in group setting. In addition, younger men are more likely to be groomed (in terms of potentially abusive and/or criminal behaviours) and that it could therefore be problematic having young men and older men together in the same group.

## 6.2 Exclusion criteria for male participants

- Men who do not have a female partner or ex-partner
- Court mandated referral to perpetrator programme
- Men who are high risk perpetrators of DVA as assessed by the intervention group co-ordinator
- Men who are deemed by the intervention group coordinator not willing to engage with the intervention.
- Participants who cannot understand the English language sufficiently well to give informed consent and to complete the questionnaires.
- Participants with a diagnosis of a mental illness that will prevent them from programme engagement, e.g. active psychosis,
- Participants with current unstable use/misuse of drugs or alcohol

## 6.3 Exclusion criteria for partners/ex-partners

- Participants who cannot understand English sufficiently well to give informed consent and to complete the questionnaires.
- Women who are deemed by the DVA support worker to be put at greater risk if they take part in the study.
- Women who are incapacitated by substance abuse or serious mental illness at time of seeking consent

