## 7 TRIAL PROCEDURES

Recruitment strategy to identify suitable men who will self-refer or be referred – (See Consort Flowchart A below).

- 1. Initial telephone discussion about study with prospective participant and what to expect
- 2. If suitable, the PIS will be sent via email or mail
- 3. Followed up by a telephone call or email within 5 days.
- 4. If wish to continue, arrange joint meeting with the DVPP coordinator.
- 5. At meeting:
  - a. Researcher explains the study and obtains informed consent from the participant to join the study.
  - b. The DVPP coordinator assesses suitability to potentially join a perpetrator programme, collects contact details for potential participant, for his current /

Protocol version 2.0 09/02/2018\_track changes

IRAS Project ID: 178666

ex-partners, and also for any mental health or substance abuse workers supporting the potential participant.

- c. Researcher asks participant to complete male baseline questionnaires.
- d. Participant is randomised and immediately informed of results.
- e. If man is in intervention arm, what happens next will be explained and work with intervention coordinator to ensure arrangements are understood.
- f. If man is in control arm what happens next will be explained.
- g. Supply a timeline of when to expect reminder contact and questionnaires for 3, 6 and up to 9 months to all.
- 6. Follow up contact with current or ex-partner and explain study (See Consort Flowchart B below). Check when the last contact with her partner occurred and ask about frequency of contact. If agrees to take part, arrange to meet if safe and check study understanding, obtain consent.
- 7. At meeting with female partner/ex-partner:
  - a. Complete female baseline questionnaires
  - b. Inform current or ex-partner of male's allocation to randomisation arm and contact women's worker appropriate to trial arm (dedicated worker intervention arm; generic women's worker control arm).
  - c. Supply a timeline of when to expect reminder contact and questionnaires for 3, 6 and up to 9 months to all.

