Female current partners or ex-partners will be contacted by the research team initially by letter, to be followed up by either a phone call, email or further letter, using contact details provided by the male partner/ex-partner. At this point, women will be asked when the last contact with her partner was and what frequency of contact occurs. Women who meet the inclusion criteria and who agree to participate will be provided with dedicated support if the partner or ex-partner has been allocated to the intervention arm or will be signposted to relevant services if she declines to participate or if her partner or ex-partner has been allocated to the control arm.

22

CONSORT Flowchart: A 2 Trial of a group programme intervention for men who are concerned about their behaviour. Recruitment Strategy: Men

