# 15.4 Appendix 4 – Schedule of Procedures

Procedures	
Informed consent	1
Eligibility assessment	1
Risk assessment	1
Randomisation: Intervention attend DVPP – men; support for women Control men (questionnaires only) Control women, support signposted	Up to 26 weekly visits of a DVPP. Reminder phone calls when questionnaire is being sent out.
Baseline questionnaires	In person
3 month questionnaires	Post or in person
6 month questionnaires	Post or in person
9 month questionnaires	Post or in person

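### The safety exclusion for women in section 6.3 rests on a DVA support worker who, in the written steps, appears only after consent, baseline and disclosure of allocation, and who differs by arm

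*Protocol*

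**What the plan says.** Section 6.3 lists as an exclusion for partners and ex-partners: "Women who are deemed by the DVA support worker to be put at greater risk if they take part in the study". It names one judge, the DVA support worker.

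Section 7.1 gives first contact to the researchers: "Female current partners or ex-partners will be contacted by the research team initially by letter". Section 7, step 6, continues: "If agrees to take part, arrange to meet if safe and check study understanding, obtain consent". Step 7a is "Complete female baseline questionnaires". Step 7b is to tell the woman the man's allocation and then "contact women's worker appropriate to trial arm (dedicated worker intervention arm; generic women's worker control arm").

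Section 7.2 confirms that she learns the allocation after her own recruitment, and adds that women who decline are told as well, for safety reasons.

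On control-arm women the text differs by place. Step 7b gives them a generic worker. Section 7.1 says they will be signposted to services, and Appendix 4 has "Control women, support signposted". Section 5 says, without separating the arms: "Partners or ex-partners of male participants who consent to join the study will be contacted by a DVA advocate based in Next Link".

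**The concern.** An eligibility criterion has to be applied before entry. Section 12.4 undertakes not to enrol anyone knowingly who fails the eligibility criteria. Here the person named to apply the criterion does not appear in the procedure until the woman is already a participant.

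Two things are at stake. The first is safety: the criterion exists to keep out women for whom taking part raises risk, and it cannot do so if it is applied after they have taken part. The second is the meaning of the women's data. A removal at 7b comes after randomisation, with the arm known, by an assessor chosen according to arm. Women's recruitment and follow-up feed the progression decision (section 7.8) and the choice of whose abuse report becomes the main-trial primary outcome (section 7.3). Outcomes are also to be tabulated by arm (section 9). If the criterion is applied differently in the two arms, the women behind those figures may be selected differently.

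**Working it through.** The check is mainly a comparison of passages; the only arithmetic is a set of bounds.

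**1. Order of events for the woman**

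| Order | Event | Source | Who acts |
|---|---|---|---|
| 1 | Man randomised and told his arm | Section 7, step 5d | Researcher |
| 2 | First letter to the woman | Section 7.1 | Research team |
| 3 | Meeting if safe; consent | Step 6 | No safety assessor named |
| 4 | Baseline questionnaires | Step 7a | Woman, at the meeting |
| 5 | Allocation disclosed to her | Step 7b; section 7.2 | Research team |
| 6 | Women's worker contacted | Step 7b | Worker chosen by arm |

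No row contains the section 6.3 judgement. The earliest row with a worker who could make it is row 6, after consent, baseline and disclosure. Because the worker is chosen by arm, she or he can infer the allocation.

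**2. Who could apply the criterion in each arm**

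- Intervention: a dedicated worker (step 7b), consistent with the dedicated support in section 7.1.
- Control: a generic worker (step 7b), or signposting only (section 7.1 and Appendix 4). On the first reading the assessor differs from the one in the other arm. On the second, no control-arm assessor is identified.

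**3. Whether another safeguard does the same job**

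- The safety condition in step 6 concerns the meeting. It names no assessor and does not ask whether participation raises her risk.
- Section 7.7 withdraws a participant once participation is known to increase danger. The chief investigator and programme manager decide, with the DMEC and the programme facilitators. It acts after entry and is not the support worker's judgement.

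**4. Bounds**

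- Women who could pass through rows 3 to 5 before a worker appears: 72 − 36 = 36 at most, or 24 + 12 by arm under 2:1 allocation, if every man's partner enrols.
- The protocol gives no share of women expected to meet the exclusion, so neither a number removed nor a difference between arms can be calculated.
- What can be shown is the weight of one classification in the section 7.8 criterion of 0.5 for women. With 36 enrolled, 0.5 × 36 = 18 followed up. If one woman not followed up is treated as an exclusion and leaves the denominator, the figure becomes 18 / 35 = 0.514, a change of 1.4 percentage points. With an assumed 18 enrolled, 9 / 18 = 0.500 becomes 9 / 17 = 0.529, a change of 2.9 points. This shows sensitivity per woman; it does not predict how many there would be.

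**The case against.** The strongest reply is that the deciding material is elsewhere. Step 6 refers to Flowchart B for the women's pathway, and sections 2.1 and 5 refer to the SOP in Appendix 1. Neither is in the available text, and either may put a worker's check before consent. That stands as a limit on the conclusion. If they do, the numbered steps in section 7 still give a different order and need to be brought into line.

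Section 5 can also be read as Next Link contacting the partners of all men who consent, in both arms and perhaps before the woman consents. The sentence does not settle whose consent is meant, gives no timing and gives Next Link no eligibility role, so it supports neither side. The DVA support worker, women's worker and DVA advocate are nowhere defined as one role or as three. If they are distinct, no written step involves the person named in section 6.3.

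A reader might infer that women can be removed in the intervention arm only, and that no control-arm woman is ever assessed. The protocol does not support that. Step 7b provides a generic worker for control-arm women, section 10.1 mentions a women's worker needs assessment without limiting it by arm, and signposting describes support rather than ruling out assessment. The supportable statement is that the passages conflict, leaving control-arm application unclear.

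A reader might also treat disclosure of allocation as itself the fault. It is not: section 7.2 discloses deliberately, even to women who decline, and the man has known his arm since step 5d.

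Finally, the analysis is descriptive (section 9) and the women's follow-up criterion is pooled over arms (section 7.8). No between-arm effect estimate is at risk in this pilot, which limits the statistical consequence. It does not touch the timing of a safety exclusion.

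**Conclusion.** The point holds for the written procedure. Followed as written, the section 6.3 exclusion is applied after consent, baseline and disclosure, by a different kind of worker in each arm, and section 7.1 and Appendix 4 leave it unclear whether it is applied at all in the control arm. This is a conflict between an entry criterion and the stated order of steps, and goes beyond missing detail. Neither the safety condition in step 6 nor withdrawal under section 7.7 replaces it.

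The order applies to every woman enrolled, at most 36. The number who would meet the exclusion, and any resulting difference between arms, cannot be stated from the protocol. The conclusion assumes that the women's worker in step 7b is the DVA support worker in section 6.3, and that Flowchart B and the Appendix 1 SOP do not already place the check earlier.

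**What to change.** Reconcile sections 5, 6.3, 7 (steps 6 to 7b) and 7.1 and Appendix 4 with one another and with Flowchart B and the Appendix 1 SOP, so that:

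- the section 6.3 judgement is made inside step 6, before consent is taken (a new step between 6 and 7 would come too late, because step 6 already ends with consent);
- it is made in the same way in both arms, by a worker whom the study team has not told the allocation;
- the result goes on the screening log, where section 7.1 already requires reasons for ineligibility;
- risk that emerges after entry is handled and counted as a withdrawal under section 7.7, not as an exclusion;
- one term is used for the worker throughout, or the roles are defined.

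Concealment from the worker can only cover what the study team discloses. The man already knows his arm, so the woman may know it too and mention it. How risk is judged is for the clinical and safeguarding leads and is not addressed here.

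The cost is a protocol amendment and a log field. Worker contact already exists at step 7b and moves earlier, with a short delay before the women's baseline and a brief contact for some control-arm women who might otherwise only have been signposted.
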